### 2. Abstract:

The present study investigates the effects of an exercise intervention on neurological correlates of aging with sedentary older adults. Whereas chronological age measures the number of days a person has been alive, biological age refers to an individual's immediate state of health in relation to the average individual across age groups. As progressive biological aging in sedentary adults is associated with declines in the neurological motor system, an important application of aging-related research is the identification of treatment interventions that may slow, stop or even reverse the biological aging process.

Aerobic exercise may exert such anti-aging effects on the neurological system, particularly in relation to patterns of interhemispheric communication. Recent studies by the principal investigator have indicated that aerobic activity level might maintain upper extremity motor performance. This study extends the previous cross-sectional research using a direct exercise intervention to measure effects on upper extremity function and patterns of motor activity within the brain.

The current study proposes to use modern neuroimaging (functional magnetic resonance imaging [fMRI] and diffusion tensor imaging [DTI]) and neurophysiological (transcranial magnetic stimulation [TMS]) techniques to investigate the effects of aerobic exercise on aging related changes of the neurological system. We will recruit 40 older, sedentary individuals. Our previous research has indicated that aging is associated with a loss of interhemispheric inhibition present in TMS (duration of the ipsilateral silent period) and during the performance of unimanual tasks in fMRI. We hypothesize that, initially, the sedentary adults will show patterns of motor activity in TMS and fMRI consistent with that of older adults, whereas after training, brain activity will be more reflective of patterns typically seen in younger adults.

Outcome measures will include changes in the battery of upper extremity motor function tests which target dexterity, psychomotor speed and reaction time. For experimental design, we will examine the effects of both aerobic exercise and dexterity training. This will be a cross-over design whereby some participants receive aerobic exercise training prior to dexterity training and others will receive dexterity training prior to aerobic exercise training. This will allow us to differentiate the effects of each type of training on motor performance and neurophysiological function.

### **3. Introduction and Background: Aging, Interhemispheric Communication and Motor Performance**

Older adults frequently complain of increased clumsiness and slowing reaction times in the upper extremity. Motor performance measures such as reaction time (Salthouse, 1984), psychomotor speed (finger tapping) (Salthouse, 1996; Cullum et al., 1989), fine dexterity (Poston et al., 2003; Carmeli et al., 2003; ) and reach accuracy (Sarlegna, 2006; Christou, 2011; Kornatz et al., 2005) all show decreases with advancing age. While some individuals find such loss of function a mere annoyance or slight embarrassment, many individuals suffer more severe consequences including loss of job responsibilities or social withdrawal. Behavioral interventions have been shown to improve motor performance (Poston et al., 2003; Christou et al., 2011), but the retention of these improvements tend to be short-lived (Carvalho et al., 2009).

Recent evidence has indicated that upper extremity performance declines in older age and may be related to changes in levels of interhemispheric inhibition of the primary motor cortices (Langan et al., 2010; Fling & Seidler, 2011; Bernard & Seidler, 2011). During volitional movement of a single upper extremity, the contralateral primary motor cortex exhibits an increase in metabolic activity consistent with increased synaptic function. However, in young adults in particular, the activity level of the opposite primary motor area tends to decrease as compared to baseline levels (inactivity). fMRI has been used to probe patterns of motor cortical recruitment during unimanual activity and increasing evidence shows that older adults tend to show increases in BOLD activity in bilateral primary motor areas during such movements (Riecker et al., 2006; Talleli et al., 2008a; Ward et al., 2008; [name] et al., 2009, 2011). However, the use of fMRI in the description of interhemispheric and intracortical patterns of communication is a relatively recent development for investigation of the human neural motor system, however. Over the past twenty years, the standard technique for motor systems inquiry has been the use of TMS, which directly investigates neural response while offering excellent temporal resolution. Interestingly aging-related studies of interhemispheric communication have employed this modality and yielded analogous findings to investigations involving fMRI. For example, using a paired-pulse TMS paradigm, Peinemann et al., (2001) reported decreases in levels of interhemispheric inhibition across increasing age, a finding later replicated by Talleli et al. (2008a; 2008b). Using a separate, but related measure called the ipsilateral silent period, Sale and Semmler (2005) reported that their elderly volunteers reported a significantly shorter duration of ipsilateral inhibition; a finding recently replicated by Fujiyama et al., (2009) and previous work by the PI ([name] et al., 2011).

In aging adults, recent work has shown that the decline in unimanual motor performance in older adults is associated with decreased duration of the ipsilateral silent period ([name] et al., 2011; Fling et al., 2011) and changes in excitability of the ipsilateral hemisphere (Bernard & Seidler, 2011; Langan & Seidler, 2010). The implication of these findings is that aging is associated with decreased interhemispheric inhibition which may be driving declines in motor performance. For example, Bernard & Seidler used transcranial magnetic stimulation to measure motor evoked potentials in the ipsilateral cortex of younger and older adults. The group found that older adults had larger motor evoked potentials in the ipsilateral cortex indicating a decrease in interhemispheric inhibition as compared to younger adults. Importantly, the group also found a somewhat proportional increase in reaction time in the older group respective of the group differences in evoked response amplitude. In our own lab, we have recently shown that duration of ipsilateral silent period, also associated with interhemispheric inhibition, is negatively correlated with age in sedentary older adults ([name] et al., 2011). Further, work from a recent project has shown that sedentary individuals even in mid-life (40-60) show decreases in duration of ipsilateral silent period and these decreases are correlated with performance on reaction time and dexterity measures (9-hole pegboard test). Further, evidence from cases of motor pathology indicates that a loss of interhemispheric inhibition is associated with increases in performance detrimental mirror movements. For example, individuals with Klippel-Feil (Leinsinger et al., 1997) or Kallman's syndrome (Verstynen et al., 2007) have an increased incidence of mirror movement concomitant with impaired levels of interhemispheric inhibition. These disorders tend to result in debilitating mirror activity during intended unimanual activity making activities such as driving or typing difficult or impossible.

Recent evidence suggests that chronological age may not be the ultimate cause of these changes in interhemispheric communication ([name] et al., 2011; [name] et al., 2009; Talelli et al., 2008b; see also Manson et al., 2006). For example, sampling across multiple age groups, Talelli et al. (2008b) reported that while chronological age did predict a pattern of fMRI activity that is consistent with a potential loss of ipsilateral inhibition (i.e. – positive BOLD in bilateral motor cortices), the best predictor of such fMRI activity was actually measures of cortical reactivity during TMS stimulation. In their sample, numerous participants in middle age showed fMRI data that were more characteristic of patterns found in elderly populations. Additionally, these same investigators reported cortical reactivity measures typically associated with elderly brains (e.g. – TMS recruitment curve assessment). As such, the age-related changes in motor activity and upper extremity performance described above may not be inevitable consequence of age, however, and, importantly, may not be immutable in individuals. There is increasing evidence that aerobic exercise and physical fitness may be a critical component in not only slowing the onset of these changes, but also reversing them.

### **Exercise, Aging and Interhemispheric communication**

Aerobic activity has long been shown to have promise in the mitigation of age-related declines in neurophysiology. While the beneficial effects of aerobic exercise on learning and memory are well known (Vaynman & Gomez-Pinilla, 2005; Winter et al.,

2007), the use of advanced neuroimaging techniques has begun to provide valuable information about the positive effect exercise has on brain structural neuroanatomy. For example, aerobic exercise has been associated with increases in overall brain volume (Colcombe et al., 2006; Chaddock et al., 2010a; 2010b ), increases in gray matter density (Chaddock et al., 2010a; Colcombe et al., 2003) and may contribute increased density in brain white matter (Marks et al., 2007, 2010 ). Erickson et al., 2011 recently produced a very exciting recent report of the beneficial effects of physical fitness on neural health that described changes to the size of the hippocampus of individuals enrolled in a longitudinal exercise program. Individuals were enrolled in either a long-term exercise program or a stretching control. Those in the long term exercise (walking) program showed increases in the size of the hippocampus and improved cognitive performance at study conclusion as compared to age-matched individuals in a stretching control group.

Some of the most exciting research exploring aerobic fitness' effects on the aging brain has come from functional neuroimaging methodologies. Functional MRI has been recently used to investigate differences in brain activity on tasks involving prefrontal areas between individuals of varying aerobic fitness. In a recent cross-sectional study, Prakash et al., (2011) reported that older participants (>55 years) who were aerobically fit tended to show brain activation consistent with proper task performance during an interference task, while sedentary older adults, who exhibited lower performance behavioral testing and showed patterns of recruitment in the prefrontal cortex more similar to adults. A previous longitudinal fMRI investigation was completed by Colcombe et al. (2005), and targeted the direct effects of exercise intervention on sedentary populations during an executive function task. In this study, participants were either divided into a group engaging in an aerobic exercise program or a control group that engaged in anaerobic stretching. Older adults who engaged in the exercise intervention program tended to show speed and accuracy improvement in memory search tasks. Further, exercising older adults revealed changes in brain activity during fMRI of the same task that more closely resembled activation patterns characteristic of younger adults.

Importantly, there is recent evidence that indicates that regular engagement of physical activity can alter age-related changes in patterns of motor neural activity as described above. Our lab has recently reported ([name] et al., 2011) that elderly adults who engage in regular physical activity have shown decreased bilateral recruitment of the primary motor cortex during unimanual task performance in fMRI. Importantly, these fMRI changes were correlated with duration of ipsilateral silent period providing strong evidence of change in interhemispheric communication during unimanual tasks. In a recent project, preliminary data analysis shows that middle age (40-60 years), sedentary adults begin to exhibit patterns of neural activity associated with a loss of ipsilateral inhibition (see Preliminary Studies). Voelcker-Rehage et al., (2010) recently reported that elderly adults who engage in aerobic activity show decreased activity in the ipsilateral motor cortex during unimanual movement in fMRI. However, to date, we know of no investigation that has attempted to investigate the direct effects of an exercise intervention on older adults on motor cortex excitability.

From the cited findings and the PI's previous research program, the impetus behind the PI's current research program has evolved. A previous study compared the effects of long-term physical fitness on neurophysiological measures of interhemispheric inhibition that may be diagnostic of biological motor health. This study has shown that elderly adults who are physically fit may mitigate a loss of interhemispheric inhibition prevalent in sedentary older adults ([name] et al., 2011). However, the project was limited realized that like most cross-sectional aging research using advanced neuroimaging, the interpretation of findings from this study was somewhat limited due to the use of age extremes. To address this issue, the PI completed a project investigating the effects of aerobic fitness on interhemispheric inhibition in middle aged individuals. Preliminary data analysis shows that physical fitness level in middle age is associated with higher levels of motor performance ([name] et al., 2012).

The goal of the current project is to investigate the direct effect of an aerobic exercise intervention on levels of interhemispheric communication in sedentary older Veteran's and subsequent changes in motor performance. We hypothesize that an aerobic intervention will improve upper extremity motor performance and decrease or reverse losses in interhemispheric inhibition in these participants.

#### **4. Objectives**

The short term objective of this proposal is to take the next logical step of our research program and identify the effects of aerobic exercise in addition to dexterity training on upper extremity motor function using an intervention approach. Prior to any intervention, participants will undergo a self-monitored 12-week stretching program of the upper extremity. We will inquire as to physical activity level on a bimonthly basis. After this period participants will be randomized into either a 12-week exercise or 12-week behavioral training sessions (depending on group placement) both of which are expected to facilitate physiological changes.

For the 12-week aerobic exercise component of this group, participants will follow the guidelines provided by the American College of Sports Medicine for optimizing cardiovascular fitness. Drs. [name] and [name] will monitor the implementation of these guidelines. Participants will exercise 3 times a week on a stationary cycle ergometer in a group setting. We chose a lower extremity intensive exercise task to decrease potential confounds with upper extremity motor practice (such as the use of an arm cycling ergometer). The 12-week behavioral training component of the study is an adaptation of a motor training program previously shown increase dexterity, coordination and decrease motor output variability in older adults (Kornatz et al., 2005; Christou et al., 2011).

The following specific aims and hypotheses are proposed:

1. To determine the relative effectiveness of a behavioral motor training regimen versus an aerobic exercise regimen respective of upper extremity motor performance.

Consistent with the findings from previous work we expect dexterity gains in upper extremity function from behavioral training. We also expect dexterity gains after the aerobic exercise intervention.

2. To assess the effects of the aerobic activity on interhemispheric inhibition using fMRI and TMS.

We expect that aerobic activity intervention can mitigate or reverse aging-related loss of interhemispheric inhibition as measured by fMRI and TMS. We expect that behavioral training of unimanual activity acts to alter interhemispheric communication dynamics and this is a potential mechanism of improvement in motor performance.

3. To determine if role of exercise duration in maintaining or enhancing motor performance and levels of interhemispheric inhibition.

We anticipate that groups that are enrolled in the regular aerobic exercise will show maintenance or enhancement of potential gains from the other interventions. This group (n=20) will show maintained or better upper extremity performance in conjunction with increased levels of interhemispheric inhibition as compared to 9 month assessments and the no-intervention group. The no-intervention group will still show improvement as compared to their enrollment assessments.

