
After the each group has completed the first component of the study, behavioral and neuroimaging (fMRI/TMS) assessments will be completed. The groups will then switch from the exercise intervention to the behavioral or vice-versa, depending on initial assignment. The interventions will proceed as previously described within these groups for another 12-week timeframe after which imaging and behavioral assessments will again be taken to test for effect of training type and effect of reversal.

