### **Specific Aim 3) To determine if role of exercise duration in maintaining or enhancing motor performance and levels of interhemispheric inhibition.**

*Introduction:* Behavioral interventions (motor strength and coordination) have been shown to be effective in improving upper extremity motor performance in older adults (Christou, 2011; Engler et al., 2011), however the duration of these gains appear to be short-lived (Toraman, 2004; Ivey et al., 2000). After as little as a few weeks of detraining, motor strength and coordination in the upper extremity rapidly begins to return to pre-intervention levels (Carvalho et al., 2009; Toraman, 2005; Toraman & Ayceman, 2005;). Evidence from exercise interventions assessing gait and locomotion have shown that exercise programs over a longer term (>6 months) are associated with improved proprioception, fewer falls and better balance (Arnold et al., 2008). However, the comparison of outcomes of upper extremity function in elderly adults respective of exercise duration remains largely unexplored. In addition to comparing the effects of short-term exercise (3 months) versus behavioral training (3 months) on upper extremity function, the current proposal will evaluate if a longer-term (6 months) exercise program

can maintain or enhance upper extremity function and associated levels of interhemispheric inhibition. Further, we will inquire as to how the long-term exercise program has affected the general quality of life in our sample.

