**Research Design:** As shown in the figure below, the study groups will be split after the second intervention. Participants will then be either enrolled in 26 week exercise program or placed in no treatment group with no physical activity requirements other than a light stretching regimen. Participants will be given elastic Therabands during the waiting phase and asked to engage in light stretching exercises of the large muscle groups of the arms, trunk and legs (prescribed in the Theraband training manual and instructed by research associates at first assessment). During this six-month period, participants enrolled in the exercise group will continue to adhere to the exercise regimen described in detail above (participants will be provided with an exercise bike for home use). Participants in the no aerobic exercise intervention will be asked to engage in the Theraband stretching training similar to the waiting period protocol. At the end of the six months, all participants will return for a final/followup behavioral and neuroimaging assessment. At this time, participants in the no exercise intervention group will be given an exercise bicycle for home use as compensation.

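### Aim 3 claims to determine the role of exercise duration, but its arm comparison cannot separate longer exercise from still exercising at the final assessment

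*Combined protocol and SAP*

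**What the plan says.** Section 4 (Objectives) gives the third aim as "To determine if role of exercise duration in maintaining or enhancing motor performance and levels of interhemispheric inhibition", and the Specific Aim 3 heading in section 5 repeats it. The wording is deliberate. The Aim 3 introduction says that "the comparison of outcomes of upper extremity function in elderly adults respective of exercise duration remains largely unexplored", recalls the 3-month exercise and behavioral blocks, and adds that "the current proposal will evaluate if a longer-term (6 months) exercise program" can maintain or enhance function.

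The design is as follows. Each participant has 12 weeks of aerobic exercise and 12 weeks of behavioral (dexterity) training, in either order: "The groups will then switch from the exercise intervention to the behavioral or vice-versa, depending on initial assignment" (section 5, Research Plan). Under the Aim 3 Research Design, "the study groups will be split after the second intervention", and "Participants will then be either enrolled in 26 week exercise program or placed in no treatment group with no physical activity requirements" apart from light stretching. In the six months that follow, "participants enrolled in the exercise group will continue to adhere to the exercise regimen described in detail above", with a bike for home use. Then: "At the end of the six months, all participants will return for a final/followup behavioral and neuroimaging assessment".

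The Objectives expect the exercise group (n=20) to hold or improve on its 9-month values and to do better than the no-intervention group. Section 7 analyses Aim 3 with a mixed model whose fixed factors are time, treatment group and their interaction. It has no term for cumulative exercise or for time since the last session.

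**The concern.** To learn about duration, one needs people who exercised for longer and for shorter periods but are otherwise in the same state when measured. Here the longer-duration participants are measured while training and the shorter-duration participants long after they stopped. The result that the Objectives predict, the exercise group ahead of the no-intervention group, is expected if longer programmes work better. It is equally expected if only current exercise matters and the comparator has lost its gains.

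The plan gives reason to take the second explanation seriously. The Aim 3 introduction reports that upper-extremity strength and coordination begin to return to pre-intervention levels within a few weeks of detraining. That evidence concerns strength and coordination training, so carrying it over to aerobic gains or to interhemispheric inhibition is an inference. It is still a live alternative, and under the present aim a positive result would be reported as an effect of duration.

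**Working it through.** The plan gives no figure for a duration effect, so there is none to reproduce. The check is of what the design can identify.

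**Inputs.** Waiting period 12 weeks; two crossover blocks of 12 weeks each; final phase 26 weeks (section 5). Timeline: waiting period weeks 0–12, block 1 weeks 12–24, block 2 weeks 24–36, final phase weeks 36–62. The plan's nominal assessment months are 0, 3, 6, 9 and 15.

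**Exercise history at the final assessment (week 62).**

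| Order, then final phase | Cumulative aerobic weeks | Still exercising | Weeks since last aerobic session |
|---|---|---|---|
| Aerobic-first, exercise | 12 + 26 = 38 | yes | 0 |
| Dexterity-first, exercise | 12 + 26 = 38 | yes | 0 |
| Aerobic-first, none | 12 | no | 62 − 24 = 38 |
| Dexterity-first, none | 12 | no | 62 − 36 = 26 |

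**Duration against still exercising (yes = 1, no = 0).** In every row, cumulative weeks = 12 + 26 × (still exercising). The correlation is 1.0, and the matrix with columns [1, duration, still exercising] has rank 2 of 3. No row has long exposure followed by a stop, and none has 12 weeks with exercise still under way.

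**Duration against weeks since last session.** The three distinct rows [1, duration, weeks since] are (1, 38, 0), (1, 12, 26) and (1, 12, 38). The determinant is (12 × 38 − 26 × 12) − 38 × (38 − 26) = 144 − 456 = −312, so the rank is 3 of 3. Coded in weeks, the two are not perfectly aliased. But recency varies at fixed duration only between 26 and 38 weeks, within the comparison arm, where it coincides with training order. Using it means extrapolating from 26 weeks to 0.

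**All five assessments.** Take effects for the four histories (4 columns) and for time (4), plus current and cumulative terms for exercise and for dexterity training (4): 12 columns, rank 11. The dependency can be shown by hand. Compute (cumulative exercise + cumulative dexterity) − 26 × (current exercise + current dexterity):

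- Enrolment and month 3: 0 for everyone.
- Month 6: 12 − 26 = −14 for everyone.
- Month 9: 24 − 26 = −2 for everyone.
- Month 15, exercise arm: (38 + 12) − 26 = 24. No-exercise arm: (12 + 12) − 0 = 24.

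The value depends only on the visit, so the time effects absorb it and neither exercise term is estimable. If dexterity training is assumed to leave no lasting effect, the cumulative dexterity term drops out and the rank is 11 of 11. The exercise terms are then estimable, given also a linear duration effect. The plan adopts neither assumption.

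**Data at equal recency.** In the 26-week exercise arm, both orders have a visit at 12 aerobic weeks and a visit at 38 weeks, each at the end of a training period: month 9 and month 15 for dexterity-first, month 6 and month 15 for aerobic-first. With 20 in that arm and an even split by order (an assumption), that is about 10 people per order.

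**The case against.** The strongest reply is that Aim 3 speaks of maintaining or enhancing gains, and that a longer programme set against none at a fixed time is a legitimate comparison of policies. That stands: the narrower question is answerable, and what fails is the attribution to duration. Randomising the second split, whose allocation method is not stated, or modelling training order would not restore it.

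A second reply is that the Objectives already plan a comparison with 9-month values. They do, and it helps, but at month 9 the aerobic-first participants have been off aerobic exercise for about 12 weeks. Their change to month 15 therefore mixes resumption with duration. Their matching visit is month 6.

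Four stronger readings are tempting and are not supported:

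- A reader might infer that duration and recency are aliased in every sense. This holds for the arm contrast and for exercising yes/no, but not for weeks since the last session.
- A reader might infer that only dexterity-first participants give data at equal recency. The aerobic-first participants in the exercise arm do too.
- A reader might infer that the comparator will lose its gains, so that an arm difference would appear regardless. The cited detraining evidence supports only that it could.
- A reader might describe the contrast as continuing versus stopping. That fits dexterity-first; for aerobic-first it is resuming versus remaining stopped.

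The timeline is also not fully consistent. The blood-collection schedule (BDNF Evaluation) and the Daily Activity Log item under the Aim 3 measures call the last assessment a 12-week follow-up, whereas the Research Design puts it at six months. If the final phase were 12 weeks, the contrast would be 24 weeks and still exercising against 12 weeks and stopped 12 or 24 weeks earlier, so the problem would remain. The design figure could not be read here, but the text describes only two final-phase arms and one final assessment.

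**Conclusion.** The point holds for the between-arm comparison. At the final assessment, 38 cumulative aerobic weeks always go with current exercise, and 12 weeks always go with having stopped about 26 or 38 weeks before. The time, group and interaction model cannot assign a difference to duration.

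This rests on the Research Design as written: exercise continues to the end of the six months, and there is no period off exercise before the final visit. It does not depend on detraining actually occurring, only on its not being excluded.

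Aim 3 is not empty. It can address whether a further 26 weeks of exercise differs from none, and it has limited within-person data at equal recency from both training orders. The defect lies in what may be concluded, and it is worth correcting because the correction is cheap.

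**What to change.** 1. In section 4 and in the Specific Aim 3 heading and introduction, restate the aim and its conclusion as a further 26 weeks of aerobic exercise versus none after the crossover. Say that this means continuing versus stopping for dexterity-first participants and resuming versus remaining stopped for aerobic-first participants. Draw no inference about duration from the arm comparison.
2. For the 26-week exercise arm, refine the planned 9-month comparison. Report by training order, with confidence intervals, the within-person change to month 15 from the end of the 12-week aerobic block (month 9 for dexterity-first, month 6 for aerobic-first). Label it descriptive.
3. State the limits of that table: no concurrent control; elapsed time and repeat testing; the move from supervised sessions to a home bike; and, for aerobic-first, an interruption with dexterity training in between.
4. Reconcile the 12-week follow-up label in the blood-collection schedule and the Daily Activity Log item with the six-month final assessment.

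The cost is a narrower stated claim, some rewording and one extra table from visits already planned. Arms, visits and sample size do not change.
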